4.10.3.1 QOLRAD

Reflux related impact will be assessed based on the patient reported outcome (PRO) QOLRAD. The heartburn version of the QOLRAD is a disease specific instrument and contains 25 questions addressing concerns associated with gastrointestinal symptoms. Each question is scored from 1 to 7, where a higher score represents a higher (“better”) health-related quality of life.

The QOLRAD will be completed pre-dose by patients at Visits 2 (Baseline), 3 (Week 1), 4 (Week 2), 5 (Week 4), and 9 (Week 8) (see Table 1 in section 6.1).

The questions are categorized into five domains: emotional distress (six questions), sleep disturbance (five questions), vitality (three questions), food/drink problems (six questions) and physical/social functioning (five questions).

- Emotional distress (questions 12, 14, 15, 17, 19, 22)
- Sleep disturbance (questions 8, 10, 11, 18, 21)
- Food/drink problems (questions 3, 5, 9, 13, 16, 20)
- Physical/social functioning (questions 2, 6, 23, 24, 25)
- Vitality (questions 1, 4, 7)

For the calculation of domain scores, in case of missing items, these missing items can be replaced under specific conditions (the half-scale method) as follows:

- If 50% or more of the questions in one dimension are completed, the mean value of the completed items should replace the missing responses.

- If less than 50% of the questions in one dimension are completed, the missing responses will not be replaced.

The score in each domain will be calculated as the mean of all items in that domain, only if all items are not missing after replacement.

To evaluate the reflux related impact pattern during the initial 4 weeks treatment and the subsequent additional 4 weeks (Weeks 5-8) open-label treatment with lansoprazole 30 mg QD, the following summaries will be provided by study treatment group and assessment day:

- A summary of QOLRAD domain scores and change from baseline (FAS/PP)
- A plot of QOLRAD domain scores at baseline and Week 1, Week 2, Week 4 and Week 8 (FAS/PP).

A listing of QOLRAD results will be provided. Original values and imputed values will be provided, together with domain scores.

4.10.3.2 mRESQ-eD

Reflux related symptoms will also be assessed based on the modified RESQ-eDiary. mRESQ-eD contains 8 items where 5 items assess severity (Did not have – Severe) and 3 items assess frequency (Never – Very often) of symptoms.

- Heartburn domain (questions 1, 2) assess severity (0=Did not have, 1=Very mild, 2=Mild, 3=Moderate, 4=Moderately severe, 5=Severe).
- Regurgitation domain (questions 6, 7, 8) assess frequency of symptoms (0=Never, 1=Rarely, 2=Sometimes, 3=Often, 4=Very often).
- Difficulty swallowing (question 3) assess severity of symptoms (0=Did not have, 1=Very mild, 2=Mild, 3=Moderate, 4=Moderately severe, 5=Severe).
- Hoarseness (question 4) assess severity of symptoms (0=Did not have, 1=Very mild, 2=Mild, 3=Moderate, 4=Moderately severe, 5=Severe).
- Cough (question 5) assess severity of symptoms (0=Did not have, 1=Very mild, 2=Mild, 3=Moderate, 4=Moderately severe, 5=Severe).

Patients will be asked to report their symptoms every 12-hours, once before the morning dose and once before the evening dose of the IMP through week 1 to week 8.

Missing values will be imputed if possible.

Imputation of missing values:

For each item, morning recordings will be regarded as one sequence of observations and evening recordings as another sequence of observations. Missing values in the sequence of morning or evening recordings respectively will be imputed according to the following rules:

- If a single observation is missing, the missing value will be replaced by the larger of the two surrounding values.
- If two or more consecutive observations are missing the values will remain missing.

Item values of severity or frequency for a day (approximately a 24 h period) will then be constructed using the imputed sequences of evening and morning recordings of severities or frequencies. A day will consist of the morning and evening recording of each day starting on Day 1, the day after the first treatment intake. All recordings taken on the day of first treatment intake will be considered as Day 0 recordings. There could be some pre-dose recordings and some post-dose recordings depending on the time the patient had the first dose.

- The daily item severity or frequency will be defined as the maximum of the two recordings.
- If either the morning or the evening recording is missing, the daily value will be set to the available value.
- If both morning and evening recordings are missing, the daily value will be set to missing.

Baseline morning, evening and 24-hour daily recording will be defined using the recordings prior to the first treatment dose, if these recordings are available.

Domain scores:

The domain severity or frequency on a given day, morning or evening will be derived as the highest severity or frequency of the items that form the domain. If some items are missing, the highest value will be chosen amongst available items.

Heartburn domain:

- Morning score: the highest severity score between item 1 and item 2 of the morning assessment (min-max 0-5).
- Evening score: the highest severity score between item 1 and item 2 of the evening assessment (min-max 0-5)
- Daily score: the highest severity score between daily assessments of item 1 and item 2 (min-max 0-5)

Regurgitation domain scores are constructed in the same way as Heartburn domain using the items that form the domains.

Weekly means of the daily scores, of the morning scores and of the evening scores will then be calculated and presented by week for each domain or item. A minimum of 4 days during a week with severity or frequency of symptoms recorded is required to calculate weekly means for all the 3 domains.

Heartburn free:

Heartburn-free in a 24-hour day is defined as a daily score of 0 for the heartburn domain, and the number of heartburn-free days over a week will be calculated. The percentage of heartburn-free days for a patient over a week will be calculated as:

% heartburn-free days = number of days with daily score =0 / number of days the severity of symptom is recorded x 100.

A minimum of 4 days during a week with severity of symptoms recorded is required, otherwise, the percentage will be set as missing for that week.

The percentage of heartburn-free in the morning and heartburn-free in the evening will also be calculated for morning and evening records respectively.

Heartburn with at most mild symptoms:

Heartburn with at most mild symptoms (either no symptoms, very mild symptoms or mild symptoms) in a 24-hour day is defined as all the items in the domain that have a daily score of maximum 2, and percentage of heartburn- at most mild symptoms days for a patient over a week will be calculated as:

% heartburn-at most mild symptoms days = number of days where all items have daily score ≤ 2 / number of days the severity of symptom is recorded x 100.

A minimum of 4 days during a week with frequency of symptoms recorded is required, otherwise, the percentage will be set as missing for that week.

The percentage of heartburn-at most mild symptoms in the morning and heartburn-at most mild symptoms in the evening will also be calculated for morning and evening records respectively.

The following summaries will be provided by study treatment group and assessment time (morning, evening or daily):

- mRESQ-eD: Summary of weekly mean domain scores/items during the Weeks 1-8 (FAS/PP)
- A plot of weekly mean domain scores/items during the Weeks 1-8 (FAS/PP)
- mRESQ-eD: Percentage of heartburn-free 24-hour days during the Weeks 1-8 (FAS/PP)
- mRESQ-eD: Percentage of heartburn-at most mild symptoms 24-hour days during the Weeks 1-8 (FAS/PP)
- A plot of heartburn-free rate from 1 to 8 weeks of treatment (FAS/PP)
- A plot of heartburn- at most mild symptoms rate from 1 to 8 weeks of treatment (FAS/PP)

Listings of mRESQ-eD results will be provided. Item scores, domain scores and weekly mean domain scores will be provided (morning, evening and daily scores).

4.10.3.3 Heartburn assessed by investigator

At each visit, Investigator will assess the severity of patients' heartburn, regurgitation and dysphagia in the 7 days prior to the visit. The assessment will include both the severity grade and the frequency of symptoms.

The potential frequency is defined as one of these grades: All of the time, Most of the time, Quite a lot of the time, Some of the time, A little of the time, Hardly any of the time and None of the time. Symptoms are scored as either none, mild, moderate or severe.

The following summaries will be provided by study treatment group and visit:

- A summary of investigator assessment of symptoms (severity and frequency of heartburn, regurgitation and dysphagia) at Weeks 1-8 (Visits 2-9) (FAS/PP)
- A bar chart of investigator assessment of heartburn (severity and frequency) at baseline and from 1 to 8 weeks of treatment (FAS/PP)
- A bar chart of investigator assessment of regurgitation (severity and frequency) at baseline and from 1 to 8 weeks of treatment (FAS/PP)
- A bar chart of investigator assessment of dysphagia (severity and frequency) at baseline and from 1 to 8 weeks of treatment (FAS/PP)

A listing of investigator assessment of symptom at Weeks 1-8 (Visits 2-9) will be provided:

4.10.4 Exploratory efficacy endpoint

CCI

CCI

[figure not shown]
Pre-dose plasma concentrations will be collected twice daily, pre-dose, before the first and the second dose administration at Day 7, Day 14 and Day 28 visits in all patients.

The following descriptive statistics will be presented for plasma concentrations obtained at each nominal time point: n, arithmetic mean, SD, coefficient of variation (CV%), geometric mean, geometric CV%, median, minimum and maximum values.

CCI

CCI

CCI

CCI

CCI

CCI

Parexel International

Cinclus Pharma AG

Protocol #CX842A2201

Statistical Analysis Plan

CC1

4.11 Safety Evaluation

All safety summaries and analyses will be based upon the Safety Set as defined in Section 4.5.

4.11.1 Adverse Events

An AE is any untoward medical occurrence in a clinical study patient administered a pharmaceutical product and which does not necessarily have a causal relationship with this treatment. An AE can therefore be any unfavorable and unintended sign (including clinically significant abnormal values from relevant tests, such as clinical safety laboratory tests, ECGs, vital signs), symptom, or disease temporally associated with the use of an IMP, regardless of whether it is considered related to the IMP.

Collection of AEs will start directly after the ICF has been signed. Only AEs related to study procedure will be collected between screening visit and the first IMP administration.

A TEAE is any AE only present after the initiation of IMP administration or any event already present that worsens in either severity or frequency following exposure to the IMP and on or before 30 days after the date of last dose of study treatment.

Where dates are missing or partially missing, adverse events will be assumed to be treatment-emergent, unless there is clear evidence (through comparison of partial dates) to suggest that the adverse event started prior to the first dose of study treatment or more than 30 days after the last dose of study treatment.

Adverse events will be coded using the Medical Dictionary for Regulatory Activities (MedDRA) Version 23.0 or higher for System Organ Class (SOC) and Preferred Term (PT).

AEs are divided into defined severity grades (Grade 1: mild, Grade 2: moderate, Grade 3: severe, Grade 4: life-threatening and Grade 5: death).

AEs are also divided into 3 different causal relationships (Probable, Possible and Unlikely). An AE is considered causally related to the use of the IMP when the causality assessment is probable or possible.

The following summaries will be provided by treatment group and overall.

- An overview table summarizing the number and percentage of patients with at least one of the following AEs together with the corresponding number of events for each of these AE categories listed below:
 - any AE,
 - any TEAE,
 - any severe TEAE,
 - any treatment related TEAE (ADR),
 - TEAE leading to discontinuation from the study,
 - Any Serious Adverse Event (SAE).
 - Any treatment emergent SAE,
 - Any treatment emergent adverse event of special interest (AESI)
- A summary of the number and percentage of patients reporting a TEAE by SOC and PT,
- A summary of the number and percentage of patients reporting a TEAE by PT by frequency of occurrence,
- A summary of the number and percentage of patients reporting a TEAE by severity, SOC and PT,
- A summary of the number and percentage of patients reporting a TEAE by causality to study treatment, SOC and PT,

All adverse event summaries will provide the number of patients reporting at least one adverse event and the total number of events reported and will be ordered alphabetically for SOC and PT within SOC.

In summary by frequency of occurrence, the preferred terms will be ordered according to the frequency of occurrence in the total column.

AEs will be counted as follows:

- In summaries of number of patients experiencing AEs, patients with more than one AE within a particular SOC are counted only once for that SOC. Similarly, patients with more than one AE within a particular PT are counted only once for that PT.
- In summaries of number of patients experiencing AEs, patients reporting a TEAE more than once within that SOC/ PT, but with different severities, the worst severity will be used in the corresponding severity summaries.

- In summaries of number of patients experiencing AEs, patients reporting a TEAE more than once within that SOC/ PT, but with different relationships, the worst relationship will be used in the corresponding relationship summaries.
- If the severity is missing for a TEAE, it will be considered as missing in the summary tables.
- If the causality is missing for a TEAE, it will be considered as missing in the summary tables.

In addition, a listing with all AEs data will be listed by treatment including non-TEAEs. Treatment-emergence status will be flagged in the listing.

AE duration will be derived with the formula:

AE duration = (AE end date - AE onset date + 1); in case of AE ongoing, the date of last contact with the patient will be used as AE end date for the scope of deriving the AE duration.

A by-patient listing of all AEs (including non-treatment-emergent events: flagged) will be provided. These listings will be presented by treatment group and will include: patient identifier, age, sex, AE (SOC, PT, and verbatim term), date of onset, date of resolution or ongoing, duration, severity, NCI CTCAE toxicity grade, seriousness, causality to study treatment, causality to non-study treatment, action taken and outcome.

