3 INVESTIGATIONAL PLAN

3.1 Overall Study Design and Plan

The study will be conducted in multiple centers in Europe and the US.

This is a phase 2, randomized, double-blind, active comparator-controlled study with a parallel group design including four arms with X842 and one arm with lansoprazole.

Approximately 240 patients with erosive esophagitis due to GERD LA grade C or D and patients with erosive esophagitis due to GERD LA grade A or B with at least partial symptom response but still endoscopically unhealed after 8 weeks history of standard treatment healing course with PPI, will be randomized in order to have 200 evaluable patients.

Randomization to one of the treatments with X842 twice daily (BID) 25 mg, 50 mg, 75 mg, 100 mg, or lansoprazole 30 mg once daily (QD) will be based on a 1:1:1:1:1 scheme. One site cannot enroll more than 20% of the overall number of patients (48 patients per site).

The duration of each patient's participation in the study, including screening, blind treatment period and open-label treatment period, will be approximately 60 days.

The patients will be randomized for 4 weeks (28 days, -2/+5 days) of double-blind treatment and will be provided with investigational medicinal product (IMP) for 35 days (including one additional blister pack dispensed at Visit 2/Day 0) to allow for treatment up to the visit window.

Pharmacokinetic (PK) blood sampling pre-dose, close before the first and the second dose administration will be performed at Day 7, Day 14 and Day 28 visits days in all patients.

[figure not shown]
All patients will have an endoscopic evaluation after 4 weeks treatment. Following the endoscopic evaluation, all patients will receive subsequent 4 weeks of open-label treatment with lansoprazole 30 mg QD. Repeated symptom evaluation to detect symptom pattern will be assessed during this period.

Randomization ratio	TREATMENT GROUP	Morning Capsule	Morning tablet 1	Morning tablet 2	Evening tablet 1	Evening tablet 2
1	X842 (BID) 25 mg	Placebo	25 mg	placebo	25 mg	placebo
1	X842 (BID) 50 mg	Placebo	50 mg	placebo	50 mg	placebo
1	X842 (BID) 75 mg	Placebo	50 mg	25 mg	50 mg	25 mg
1	X842 (BID) 100 mg	Placebo	50 mg	50 mg	50 mg	50 mg
1	Lansoprazole (QD) 30 mg	30 mg	placebo	placebo	placebo	placebo

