3.2.2 Safety Variables

- Physical examinations: assessment of head, eyes, ears, nose, throat, skin, thyroid, neurological, lungs, cardiovascular system, abdomen (including liver and spleen), lymph nodes, genitourinary system (optional) and extremities (musculoskeletal system) after 4 and 8 weeks of treatment.
- Weight and BMI after 4 and 8 weeks of treatment.
- Vital signs: Systolic and diastolic BP, heart rate (pulse), body temperature and respiratory rate after 1, 4 and 8 weeks of treatment.
- 12-lead electrocardiograms (ECG): PQ/PR, QRS, QT and QTcF intervals after 1, 4 and 8 weeks of treatment.
- Clinical laboratory tests: hematology, clinical chemistry, coagulation, and urinalysis parameters after 1, 4 and 8 weeks of treatment.
- Adverse event (AE) assessments: treatment emergent adverse event (TEAE), adverse event of special interest (AESI), serious adverse event (SAE) during the Weeks 1-8 (Visits 2-9).
- Concomitant medication assessments during the Weeks 1-8 (Visits 2-9).

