4.11.2 Adverse Events of Special Interest (AESI)

The following conditions should be considered AEs of special interest:

- a. ALT or AST $\geq 8 \times$ ULN
- b. ALT or AST $\geq 5 \times$ ULN for 2 or more weeks
- c. ALT or AST $\geq 3 \times$ ULN **and** total bilirubin $\geq 2 \times$ ULN (or ALT or AST $\geq 3 \times$ ULN **and** INR > 1.5)
- d. ALT or AST $\geq 3 \times$ ULN accompanied by clinical symptoms believed to be related to hepatitis or hypersensitivity, such as new or worsening of fatigue, nausea, vomiting, right upper quadrant pain or tenderness, fever, or rash
- e. ALT or AST $\geq 5 \times$ ULN but $< 8 \times$ ULN and cannot be monitored at least weekly for ≥ 2 week

Hy's Law, defined as $\geq 3 \times$ ULN ALT or AST **with coexisting** $\geq 2 \times$ ULN total bilirubin with no alternative explanation for the biochemical abnormality other than IMP (for example elevated ALP indicating cholestasis, viral hepatitis, other medication) must always be reported without delay as an AESI, and, if applicable, also as an SAE.

All potential AESIs will be medically evaluated during the study, before the database lock and unblinding, by the sponsor to identify events which could possibly be AESIs.

A list of PTs for AESIs will be provided for identification and AESIs will be flagged in the database.

The following summary and listing will be provided.

- A summary of the number and percentage of patients reporting an AESIs by SOC and PT.
- Listing of AESIs

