4.11.3 Deaths, Serious Adverse Events, and Other Significant Adverse Events

The following summaries will be provided by treatment group and overall.

- A summary of the number and percentage of deaths (including SAEs with fatal outcome and deaths as PT),
- A summary of the number and percentage of patients reporting a serious TEAE, by SOC and PT,
- A summary of the number and percentage of patients with TEAEs leading to discontinuation of study treatment, by SOC and PT.

The following listings will be provided:

- A listing of all deaths that occurred during the study,
- A listing of all SAEs,
- A listing of all AEs leading to discontinuation of study treatment.

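### The plan as written specifies no adverse-event table by phase, so events first occurring on open-label lansoprazole in Weeks 5-8 are counted in the X842 dose columns

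*SAP*

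**What the plan says.** SAP 3.1 states that after the Week 4 endoscopy "all patients will receive subsequent 4 weeks of open-label treatment with lansoprazole 30 mg QD". SAP 3.2.2 then sets the AE variables over Weeks 1-8 as a single period.

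For the AE tables, SAP 4.11.1 says "The following summaries will be provided by treatment group and overall", and 4.11.3 uses the same layout for deaths, serious events and discontinuations, including "A summary of the number and percentage of patients with TEAEs leading to discontinuation of study treatment, by SOC and PT". The text on ordering preferred terms shows that overall is a total column across arms. The table for events of special interest in 4.11.2 is "A summary of the number and percentage of patients reporting an AESIs by SOC and PT", with no phase named.

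An event is treatment-emergent if it begins or worsens after the first dose and "on or before 30 days after the date of last dose of study treatment". A patient counts once per preferred term. With repeated events, "the worst severity will be used in the corresponding severity summaries" and "the worst relationship will be used in the corresponding relationship summaries". None of these rules is limited to one phase.

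Protocol 9.4.8 also tabulates AEs by treatment group and overall. The SAP amendment (4.5.3) says only which analysis set carries the safety analyses.

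**The concern.** Nominally 28 of the 56 days behind each X842 column are spent on another drug. The lansoprazole column also pools two phases, but its drug does not change, so the mixing falls unevenly on the comparison of interest. It also blurs the comparison between X842 doses, because all four dose groups take the same drug in the second half.

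Relatedness does not separate the drugs. Protocol 6.1 lists lansoprazole among the study drugs, so an event judged related to open-label lansoprazole could appear as a related event in an X842 column.

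Safety of the four X842 doses is a secondary objective (SAP 2), and SAP 1 names safety data as one basis for choosing the Phase 3 dose. A table of the AE profile on X842 itself is what that decision needs, and the plan does not specify one.

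**Working it through.** **1. Is there a phase split for AEs?** The visible text was read for one.

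- SAP 4.11.1 and 4.11.3, and protocol 9.4.8: treatment group and total only.
- SAP 4.11.2 and SAP amendment 4.5.3: no phase named.
- SAP 4.2, presentation by assessment time: applies only where applicable, and names neither AEs nor phase.
- SAP 4.5, analysis by treatment received: deals with departures from the randomized treatment, not with a planned switch.
- SAP 4.9.1: the arms keep their labels in the open-label phase.

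Elsewhere the plan does split. Exposure, compliance and withdrawal from treatment are by phase (SAP 4.9.1, 4.9.2, 4.4.1), and protocol 9.4.6 summarises physical examination by period.

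**2. Do open-label events fall in the treatment-emergent window?** Inputs from the schedule of assessments: Visit 5 on Day 26-33 (nominal 28), Visit 9 on Day 53-59 (nominal 56).

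- If the last dose is the last open-label dose, the whole open-label phase is inside. SAP 4.9.1 favours this reading: it adds the phase when it means one phase, and leaves study treatment unqualified for overall duration.
- If it is the last blinded dose, the window nominally closes on Day 28 + 30 = 58, after Visit 9. The open-label phase lasts from 53 - 33 = 20 to 59 - 26 = 33 days. In the worst case the window closes on Day 26 + 30 = 56 with Visit 9 on Day 59, so 30 of 33 days (91%) are inside.

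**3. How large is the dilution?** The documents give no AE rates, so there is no figure to reproduce and the rates below are assumptions. Let pX and pL be the blinded-phase incidence on X842 and lansoprazole. Let q be the open-label incidence, equal in both arms and independent of the blinded phase, with no carry-over. Each arm has 48 patients (protocol synopsis).

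- 8-week incidence = 1 - (1 - p)(1 - q)
- Ratio = [1 - (1 - pX)(1 - q)] / [1 - (1 - pL)(1 - q)]
- Difference = (pX - pL)(1 - q)
- Share of affected X842 patients whose only event began on lansoprazole = (1 - pX)q / [1 - (1 - pX)(1 - q)]

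With pX = 19% and pL = 10% (blinded ratio 1.90, difference 9.0 points):

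| q | 8-week X842 vs lansoprazole | Ratio | Difference (points) | Only event on lansoprazole |
|---|---|---|---|---|
| 2% | 20.6% vs 11.8% | 1.75 | 8.8 | 0.8 of 9.9 patients (8%) |
| 5% | 23.1% vs 14.5% | 1.59 | 8.6 | 1.9 of 11.1 (18%) |
| 10% | 27.1% vs 19.0% | 1.43 | 8.1 | 3.9 of 13.0 (30%) |
| 20% | 35.2% vs 28.0% | 1.26 | 7.2 | 7.8 of 16.9 (46%) |

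For q = 10%: 1 - 0.81 × 0.90 = 0.271, 1 - 0.90 × 0.90 = 0.190, and 0.271/0.190 = 1.43.

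Ratios under other assumed blinded rates:

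| Blinded X842 vs lansoprazole | Blinded ratio | q = 2% | 5% | 10% | 20% |
|---|---|---|---|---|---|
| 5.1% vs 10% | 0.51 | 0.60 | 0.68 | 0.77 | 0.86 |
| 10% vs 10% | 1.00 | 1.00 | 1.00 | 1.00 | 1.00 |
| 9.75% vs 5% | 1.95 | 1.67 | 1.46 | 1.29 | 1.16 |
| 27.1% vs 10% | 2.71 | 2.42 | 2.12 | 1.81 | 1.49 |

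For a dose gradient, take blinded incidence 1 - 0.9^HR with HR = 1, 4/3, 5/3 and 2 for 25 to 100 mg: 10.0%, 13.1%, 16.1% and 19.0%. The 100-to-25 mg ratio of 1.90 then shrinks exactly as in the first table.

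**The case against.** The plan openly defines AEs over Weeks 1-8, protocol and SAP agree, and the safety objective, unlike the symptom objective, is not divided into two periods. On this view the 8-week table is a legitimate full-sequence summary that lacks a companion, not an error. That is fair, and the 8-week table should stay because it captures delayed X842 effects.

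The SAP never says outright which column an open-label onset belongs to. That is inferred from the arm labels and the absence of any reassignment rule. Table shells are not in the documents and some text is redacted, so the point concerns the plan as written. No visible text supports the opposite reading.

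The upper illustrations are generous. Open-label treatment is the comparator at the same dose for about the same time, so under a constant hazard q should be close to pL. That makes 5-10% the coherent range and 20% only an upper bound.

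Sampling error is also large. With 48 per arm, 19% vs 10% is about 9 vs 5 patients, and the log-scale 95% interval for a ratio of 1.90 is roughly 0.68 to 5.3. This limits the practical weight of a shift to 1.43, but the shift is systematic and avoidable.

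Partial cover exists. Withdrawal from treatment is tabulated by phase with its reason, liver chemistry is summarised by visit, and the listings carry onset dates. But the chemistry tables use low, normal and high, not the multiples of the upper limit that define the events of special interest, and a listing is not an incidence table.

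**Conclusion.** The concern holds. Followed as written, the plan counts events that begin on open-label lansoprazole in the X842 dose columns, under either reading of the treatment-emergent window. The effect on ratios is towards 1: they fall where X842 has the higher hazard, rise where it has the lower, and do not move where the hazards are equal. With assumed 19% vs 10%, the ratio of 1.90 becomes 1.59 to 1.43 for open-label incidence of 5-10%, within a wider range of 1.75 to 1.26. The absolute difference shrinks only by the factor 1 - q. These sizes rest on equal open-label incidence across arms, independent phases and no carry-over. The effect is small if open-label events are rare. It should be corrected because the safety comparison informs dose selection, although no formal test depends on it.

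**What to change.** Keep the 8-week tables and add TEAE, SAE, special-interest, related-TEAE and discontinuation tables by phase of onset.

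- **Double-blind:** onset or worsening from the first blinded dose to the first open-label dose, by treatment received. For patients who take no open-label drug, end the window at a stated point, for example the day after the last blinded dose, so that their follow-up matches that of patients who switch. Show their later events on a separate flagged row, since AEs are collected up to an Early Termination visit planned 4 weeks after stopping (protocol 8.4.2, SAP 1).
- **Open-label:** onset or worsening from the first open-label dose, shown by prior arm so that delayed X842 effects remain visible.
- **Rules:** define the last dose of study treatment for each phase. Apply the once-per-term, worst-severity and worst-relationship rules within phase. State one rule for partial dates and one for the switch day.
- **Switch day:** AE start times are collected (protocol 8.4.2) and dose times go on diary cards (protocol 6.4). Confirm that the time of the first open-label dose reaches the database. If it does not, assign switch-day events by a fixed rule.

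The cost is SAP wording and extra runs of existing tables, with no new data collection. Cells will be small, and some delayed X842 events will appear in the open-label table, which is why it is shown by prior arm beside the 8-week table. Because the SAP amendment was itself written after unblinding, tables added now must be labelled as not prespecified.
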